#### 8.4.3 CLASSIFICATION OF AN AE

#### 8.4.3.1 SEVERITY OF EVENT

All AEs will be graded using the CTCAE 5.0 criteria.

For AEs not included in the protocol-defined grading system (grade 1 to 4), the following guidelines will be used to describe severity.

- Mild Events require minimal or no treatment and do not interfere with the participant's daily activities.
- Moderate Events result in a low level of inconvenience or concern with the therapeutic measures.
   Moderate events may cause some interference with functioning.
- Severe Events interrupt a participant's usual daily activity and may require systemic drug therapy or other treatment. Severe events are usually potentially life-threatening or incapacitating. Of note, the term "severe" does not necessarily equate to "serious".

The grade and severity of the event will be determined using the DCT/NCI Common Terminology Criteria, CTCAE v.5.0. All appropriate treatment areas should have access to a copy of the CTCAE version 5.0. Study staff must use one of the CTCAE criteria to define the event. Adverse events not included in the CTCAE v.5.0 should be reported and graded under the "Other" adverse event within the appropriate category and grade 1 to 5 according to the general grade definitions, mild, moderate, severe, life-threatening, fatal or disabling, as provided in the CTCAE.

The event will be determined to be expected or unexpected. The determination of whether an AE is expected is based on agent-specific adverse event information provided in Pharmaceutical Information. Unexpected AEs are those not listed in the agent-specific adverse event information provided in Section 9 Pharmaceutical Information.

Based on this information, a decision will be made whether an adverse event should be reported as an expedited report (Serious Adverse Event 8.4.2) in addition to the routinely reported clinical data. All expedited adverse event reports will be submitted to the Institutional Review Board (IRB) and to the FDA.

Safety will be evaluated based on the incidence, severity, duration, causality, seriousness, and type of adverse events (AEs), and changes in the patient's physical examination, vital signs, and clinical laboratory results.

Investigators will use the NCI CTCAE version 5.0 published November 27, 2017.

(https://ctep.cancer.gov/protocoldevelopment/electronic\_applications/docs/ctcae\_v5\_quick\_reference\_5x7.pdf) to assess the severity of adverse events. Observed or volunteered Grade 3-5 adverse events regardless of treatment group or causal relationship to study drug will be recorded on the adverse event pages of the case report form.

There is a known rate of treatment-related mortality associated with induction chemotherapy in this population; in addition, severe infections are common. Therefore, adjudication that an adverse event is possibly related to the exposure, and not the disease or standard treatment (chemotherapy) will be an important role of the Protocol Monitoring Committee.

#### 8.4.3.1.1 LIST AND REPORTING REQUIREMENTS

There are 2 broad categories of reportable adverse events: 1) adverse events that are attributable to use of the device, i.e. the CliniMACS® system with CliniMACS® CD8 Reagent; and 2) adverse events that are not attributable to the use of the device. All reporting of adverse events will be carried out according to current IRB and FDA guidelines.

### 8.4.3.2 ADVERSE DEVICE EFFECTS

#### 8.4.3.2.1 HYPERSENSITIVITY REACTIONS

Use of the CliniMACS® System enables the infusion of CD8 depleted or selected cells that may contain residual amounts of unbound CliniMACS® CD8 Reagent (murine monoclonal antibody conjugated to an iron dextran moiety). Hypersensitivity reactions resulting from iron dextran therapy have been reported. The most dangerous complication is an anaphylactoid reaction similar to contrast media reactions. The anaphylactoid reaction is usually manifested during the first few minutes of the infusion (often during test dose administration). The most common hypersensitivity reaction occurring in more than 30% of patients given therapeutic levels of iron dextran is the development of arthralgia and fever within 24 to 48 hours after initiation of the intravenous therapy.

#### 8.4.3.2.2 REACTIONS MEDIATED BY HUMAN ANTI-MOUSE ANTIBODIES (HAMA)

The CliniMACS® CD8 Reagent also contains a murine monoclonal antibody. One of the problems limiting the therapeutic use of murine monoclonal antibodies (mAbs) has been the generation of HAMA and subsequent anaphylaxis.(92)The most commonly reported adverse effects have been myalgia, arthralgia, increased peripheral edema and flu-like symptoms, the latter involving fever (70% to 73%), chills (46% to 53%), chest pain and tightness (14%), wheezing (11% to 14%) and vomiting (13% to 32%).(93-95)

#### 8.4.3.3 ADVERSE EVENTS NOT ATTRIBUTABLE TO THE DEVICE

Four categories of device non-attributable adverse events will be monitored and, if necessary, reported: 1) non-hematologic toxicities; 2) GvHD; 3) DLI-induced aplasia; and 4) CRS. Reportable adverse events are defined as non-hematologic toxicities requiring hospitalization, grade 3 or 4 toxicities defined below, and grade II acute GvHD.

Adverse events that are not considered serious will be included in the annual report. Serious adverse events include any death within the first 56 days after DLI, grade 2-4 acute GvHD, DLI-induced aplasia, ≥grade 3 CRS, and any adverse event that is deemed to be significant by the PI.

Non-hematologic toxicities will be monitored daily while patient remains admitted (typically until ANC exceeds 500/microliter, which usually occurs between days 21 and 42), then at clinic visits on day 42, day 56, 6 months, and

1 year. Toxicities will be graded using the National Cancer Institute's Common Terminology Criteria for Adverse Events (CTCAE) Version 5.0.

The following is a list of categories that will not be required to be recorded unless the event becomes a grade 4:

- Allergy/Immunology
- Auditory/Hearing
- Cardiovascular (Arrhythmia)
- · Cardiovascular (General)
- Coagulation
- Constitutional symptoms
- Dermatology/Skin
- Endocrine
- Hemorrhage
- Hepatic
- Infection/Febrile neutropenia
- Lymphatics
- Metabolic/Laboratory
- Secondary Malignancy
- Sexual/Reproductive Function

A toxicity in the following categories will be captured as an adverse event if it reaches grade 3 or grade 4:

- Gastrointestinal
- Musculoskeletal
- Neurology
- Ocular/Visual
- Pain
- Pulmonary
- Renal/Genitourinary

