### **Dose-Expansion Cohorts**

Once the RP2D is reached, a total of10 patients will be treated at this dose. For the expansion cohort, patients will continue to be monitored for occurrence of DLT. If 2 of the first 5 patients or if  $\geq$  2 of 6 patients experience DLT, the PI will discuss with all study investigators and with CTEP whether further addition of patients is needed to reassess the RP2D.

Monitoring of safety and toxicity data will be captured in OnCore, Moffitt's clinical trials database.

Dose-limiting toxicities are defined as any of the following that is at least possibly attributable to the investigational treatment:

- 1. Grade 2-4 infusion toxicity
- 2. Grade 4 organ toxicity (as defined by NCI CTCAE v 5.0), not preexisting, not due to the primary malignancy, and not due to chemotherapy or infection
- 3. Grade 3 organ toxicity that does not resolve within 14 days and that is not preexisting, not due to the primary malignancy, and not due to chemotherapy or infection
- 4. Grade 2-4 acute GvHD
- Delayed neutrophil recovery: ANC >500/μl does not occur within 56 days AND measurable donor chimerism is >5%
- 6. Grade 3-4 cytokine release syndrome (CRS) (see Appendix C) (75)
  Any grade 5 reaction other than progressive disease

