# 8 STUDY ASSESSMENTS AND PROCEDURES

# 8.1 SAFETY ASSESSMENTS

Safety assessments will be as follows:

- History and physical: Initial and repeated at days 42 and 56, 6 months, and 1 year to evaluate for subjective or exam findings consistent with AEs.
- Bone marrow biopsy: Day 42 to evaluate the efficacy of the intervention. Day 42 bone marrow biopsy may
  be performed earlier than the day 42 if the subject has recovered from aplasia, defined as recovery of the
  ANC >500/μl.
- Peripheral blood and bone marrow chimerism: To rule out donor engraftment and confirm rejection of the
  DLI product, donor cell chimerism will be measured after neutrophil recovery (ANC ≥ 500/µI) or on day 42
  +/- 3 days after infusion. Engraftment is necessary for GVHD, so product rejection increases the long term
  safety of the product.
- Complete blood count (CBC): 3 times per week until ANC recovers to 500. Weekly through day 56. This assessment is necessary to monitor for hematologic toxicity.
- Comprehensive metabolic panel (CMP): Weekly through day 56 to evaluate for toxicity to the liver, kidneys, or electrolyte derangements.

- C Reactive Protein (CRP) and Ferritin: Weekly through day 56 to screen for evidence of cytokine release syndrome (CRS)
- Cytomegalovirus polymerase chain reaction (PCR): Weekly through day 56 to monitor for CMV reactivation while awaiting immune reconstitution.

	Initial	Allowable time from start of induction	Starting Day 0	Day 28	Day 42	Day 56	6 months +/- 2 weeks	1 yr +/- 2 weeks
History and physical	Х	Within 30 days			Х	Х	X	Х
Performance status	Х	Within 30 days						
Staging Bone Marrow Biopsy and aspirate for research	Х	Within 30 days			Xa			
Peripheral blood for research	Х		Daily days 0-7		Xa			
CBC & Diff	×	Within 7 days	ANC<500- 3x/week  ANC≥500- weekly to day 56		×	×	х	х
СМР	Х	Within 7 days	Weekly to day 56		Х	Х	Х	Х
CXR or Chest CT	Χ	Within 30 days						
Pregnancy test (women, childbearing age)	Х	Within 30 days						
Human Immunodeficiency Virus	Х	Within 30 days						
EKG	Х	-						
MUGA or ECHO	Χ	Within 30 days						
HLA typing	Х							
Anti-donor HLA antibody testing	Х				Х			
Adverse Event Monitoring			Weekly to day 56		Х	Х	X	Х
GvHD evaluation			At onset, weekly until resolves		х	х		
Peripheral blood or bone marrow for donor chimerism			If suspected GvHD		Xa	Xp		
CMV IgG	X	Within 30 days						
CMV PCR			Weekly through day 56					
C Reactive Protein	Х	Within 7 days	Weekly through day 56					

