# 8.4.4 TIME PERIOD AND FREQUENCY FOR EVENT ASSESSMENT AND FOLLOW-UP

The occurrence of an AE or SAE may come to the attention of study personnel during study visits and interviews of a study participant presenting for medical care, or upon review by a study monitor.

AEs can be spontaneously reported or elicited during open-ended questioning, examination, or evaluation of a patient.

Grade 3-5 AEs, including local and systemic reactions not meeting the criteria for SAEs, will be captured on the appropriate CRF. Information to be collected will include event description, time of onset, clinician's assessment of severity, relationship to study product (assessed only by those with the training and authority to make a diagnosis), and time of resolution/stabilization of the event. All AEs occurring while on study must be documented appropriately regardless of relationship. All AEs will be followed to adequate resolution.

Any medical condition that is present at the time that the participant is screened will be considered as baseline and not reported as an AE. However, if the study participant's condition deteriorates at any time during the study, it will be recorded as an AE.

Changes in the severity of an AE will be documented to allow an assessment of the duration of the event at each level of severity to be performed. AEs characterized as intermittent require documentation of onset and duration of each episode.

All events beginning with start of study intervention until the first event of either starting allogeneic transplant conditioning, confirmed disease relapse, death, or 1 year from the of the trial cell infusion will be reported. At each study visit, the investigator will inquire about the occurrence of AE/SAEs since the last visit. Events will be followed for outcome information until resolution or stabilization.

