#### 8.4.5 AE REPORTING

The PI and/or the research nurse will monitor each patient closely for the development of adverse events and toxicities and record all such events. AEs will be recorded and reported in our annual report. As some toxicities are expected from the chemotherapy, we will compare incidence of toxicities to historical experience when using chemotherapy without the investigational DLI product. The FDA require the timely reporting of adverse events (including toxic deaths).

Each individual sign or symptom must be documented separately. Grade 3-5 adverse events (both expected and unexpected) will be captured on the appropriate study-specific CRFs.

An investigator must verify the attribution of all adverse events. Evaluation of laboratory toxicities may be documented on CRF provided the investigator signs it. However, if an action was conducted due to this abnormality (e.g., red blood cell transfusion due to low hemoglobin) this would be recorded on the AE form also.

AE reporting will begin at the time of cell infusion and continue through 1 year from day 0 or until loss to followup, death, disease progression, or proceeding to allogeneic BMT, whichever comes first. Subjects who proceed to allogeneic BMT will come off of the trial and will no longer be followed for AEs.

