- 3. Grade 3 organ toxicity that does not resolve within 14 days and which is not preexisting, not due to the primary malignancy, and not due to chemotherapy or infection
- 4. Grade 2-4 acute GvHD
- Delayed neutrophil recovery: ANC>500/μl does not occur within 56 days AND measurable donor chimerism is >5%
- 6. Grade 3-4 CRS; see Appendix for grading scheme)
- 7. Any Grade 5 reaction other than progressive disease.

If 2 or more of the first 6 patients on any dose level experience DLTs, accrual to the trial will be suspended and the sponsor of the IDE (the PI) will initiate a formal consultation with the FDA in order to determine whether the

CD8-depleted non-engrafting HLA antigen-mismatched unrelated donor lymphocyte infusion... Protocol <20042> Version 10 29 March 2023

observed toxicities are or are not attributable to the device. Subsequent accrual to the trial may resume only with permission from the FDA. Any questions or concerns as to the relationship of grade > 3 toxicities to use of the investigational device will be discussed with the appropriate FDA Clinical Review Staff.

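### Section 8.4.3.3 waives recording below grade 4 in 15 toxicity categories, although three other sections require all grade 3-5 events and one DLT item counts prolonged grade 3 organ toxicity

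*Combined protocol and SAP*

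**What the plan says.** All references are to the combined protocol and SAP.

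**The waiver.** Section 8.4.3.3 introduces a list of 15 categories with the sentence "The following is a list of categories that will not be required to be recorded unless the event becomes a grade 4". The list includes hepatic, two cardiovascular groups, dermatology, coagulation, endocrine, hemorrhage and metabolic/laboratory. A second list of 7 categories, including renal, pulmonary and gastrointestinal, is captured from grade 3.

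**The general rule.** Three sections set a lower threshold, and none refers to the list:
- Section 8.4.3.1: "Observed or volunteered Grade 3-5 adverse events regardless of treatment group or causal relationship to study drug will be recorded".
- Section 8.4.4: "Grade 3-5 AEs, including local and systemic reactions not meeting the criteria for SAEs, will be captured on the appropriate CRF". The same section adds "All AEs occurring while on study must be documented appropriately regardless of relationship".
- Section 8.4.5: "Grade 3-5 adverse events (both expected and unexpected) will be captured on the appropriate study-specific CRFs".

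**The DLT definition.** The third item in Section 6.1.4 reads in part "Grade 3 organ toxicity that does not resolve within 14 days and that is not preexisting". Appendix F repeats it as "Grade 3 organ toxicity that does not resolve within 14 days and which is not preexisting". Both versions exclude toxicity due to the malignancy, chemotherapy or infection, and both require at least possible attribution to the investigational treatment.

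**Laboratory monitoring.** Section 8.1 schedules the comprehensive metabolic panel "Weekly through day 56 to evaluate for toxicity to the liver, kidneys, or electrolyte derangements".

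**Timing of toxicity checks.** Section 6.1.3.1 has non-hematologic toxicity assessed weekly to day 42. Section 8.4.3.3 has it monitored daily in hospital and then at visits on days 42 and 56, 6 months and 1 year. The synopsis has weekly visits after discharge to day 56. The schedule of activities (Section 1.3, repeated in 8.1) has adverse-event monitoring weekly to day 56. Under Section 9.4.2 and Appendix F the DLT window can run to day 56.

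**The concern.** A grade 3 hepatic event that is not attributed to the device is mandatory on the CRF under three sections and optional under a fourth. Section 8.4.3.3 is the more specific text, so a data manager could reasonably treat it as an exception to the general rule.

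The threshold matters because DLT item 3 operates at grade 3 and depends on duration. To apply it, someone needs the grade, the onset and the resolution of the event. In the listed categories, 8.4.3.3 does not require a record at that grade.

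Three uses of the data are exposed. The MTD is the only primary endpoint and rests on DLT counts. The expansion cohort's stopping rule in Section 9.4.4 counts DLTs. Occurrence of adverse events is a secondary endpoint, and Section 8.4.5 plans to compare toxicity incidence with historical chemotherapy experience.

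**Working it through.** The plan states no figure for this point, so there is none to reproduce. The check compares the texts and then traces the direction of the effect.

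**1. Does the section heading separate the rules?** Section 8.4.3.3 covers events not attributable to the device. Section 8.4.3.1.1 divides all reportable events into device-attributable and not. Toxicity of the infused cells, which dose escalation is meant to detect, falls in the second group. Section 8.4.3.1 applies whatever the causal relationship, and 8.4.4 and 8.4.5 carry no such limit. The rules therefore cover the same events.

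**2. Which categories can feed DLT item 3?** Not all 15. Item 3 excludes infection, and constitutional symptoms and secondary malignancy are doubtful as organ toxicity. That leaves at most 15 - 3 = 12. This is an upper bound, since others, such as metabolic/laboratory, are arguable. Hepatic, cardiovascular, skin and coagulation toxicity are plain candidates.

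**3. Do other DLT items cover the gap?** Only partly. Grade 4 organ toxicity, acute GvHD, delayed neutrophil recovery, grade 3-4 CRS and grade 5 events are unaffected by the list. But Section 8.4.3.3.1 requires biopsy confirmation of acute GvHD, so an unconfirmed grade 3 skin or liver event would have to count under item 3. Appendix C states that organ toxicities do not alter the CRS grade, so prolonged grade 3 hepatic toxicity alongside grade 2 CRS is not caught by the CRS item.

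**4. One panel, two thresholds.** The metabolic panel looks for liver, kidney and electrolyte toxicity. Renal toxicity is captured from grade 3. Hepatic and metabolic/laboratory toxicity are on the grade-4-only list.

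**5. Direction of the effect.** An omitted event can only reduce a DLT count. Under Section 9.4.2, one unrecorded DLT has these effects:
- At levels 1 and 2, 1/3 read as 0/3 means escalation instead of 3 more patients at that level. At level 3 there is no further escalation, and the table in Section 6.1.4 requires at least 6 patients at the recommended phase 2 dose.
- At any level, 2/3 read as 1/3 means 3 more patients instead of a finding that the dose exceeds the MTD.
- 2/6 read as 1/6 means escalation at levels 1 and 2, and at level 3 a declared MTD of level 3 instead of level 2.
- 3/3 read as 2/3, or 1/6 read as 0/6, changes nothing.

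In the expansion cohort, Table 1 of Section 9.4.4 acts at 2 DLTs in 3 patients, 3 in 4-6 and 4 in 7-10. A patient group exactly at a boundary would fall one short.

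**6. Assessment timing.** Section 8.4.3.3 expects neutrophil recovery, and so typically discharge, between days 21 and 42. Read alone, discharge on day 21 leaves 42 - 21 = 21 days to the next listed visit, longer than the 14 days in item 3. Section 6.1.3.1 read alone stops 56 - 42 = 14 days before the latest end of the DLT window. The weekly checks to day 56 in the synopsis, Section 1.3 and Section 8.1 cover both gaps, so this is a matter of bringing two sections into line.

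**The case against.** The strongest reply is that the rules can all be obeyed together. Section 8.4.3.3 lifts a requirement to record; it does not forbid recording, and it leaves monitoring and CTCAE grading in place. Recording every grade 3-5 event satisfies all four sections. This is correct, and on that practice nothing is lost. It does not cure the plan, because staff who follow 8.4.3.3 as written would be working within the protocol while under-capturing data for the primary endpoint.

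The second reply is that a prolonged grade 3 organ toxicity would usually surface elsewhere. Much of this stands:
- Section 8.4.2 makes events that require or prolong hospitalization, or are medically significant, SAEs followed to resolution or stability. Section 8.4.3.3 adds any event the PI considers significant.
- Section 8.4.5 allows laboratory toxicities to be documented on a CRF signed by the investigator, and weekly panels would show grade and approximate duration for liver and electrolytes. The panel example is therefore better evidence of inconsistent thresholds than of lost DLTs.
- Appendix F bars escalation until patients have been fully assessed for DLTs, and Section 10.1.5 provides continuous monitoring by the PI and team.
- Section 10.1.5 also refers to a data and safety plan that will define DLTs. Neither that plan nor the CRFs are among the documents.

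These routes would catch many such events, but no section describes a separate DLT record that overrides the list. The Protocol Monitoring Committee reviews adverse-event patterns (Section 6.4) and has a role in attribution (Section 8.4.3.1). An event never recorded may not reach it.

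**Conclusion.** The recording rules contradict each other and should be reconciled. If 8.4.3.3 is followed, a prolonged grade 3 organ toxicity in some of the 15 categories may be absent from the adverse-event data. The effect on DLT counts could run only downward, and the adverse-event endpoint would be under-reported.

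The size cannot be estimated. The documents give no rate for these events and no basis for the share that would be missed. The loss is zero if 8.4.3.1, 8.4.4 and 8.4.5 govern, and otherwise limited by the safeguards above. The conclusion assumes only that some staff might treat the list as an exception.

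A reader might infer more, and the documents do not support it:
- That the MTD will be set too high. This needs an event that meets item 3, goes unrecorded, escapes the other routes and falls where one DLT changes the decision. Any probability of over-escalation would rest on an invented missed share.
- That all 15 categories bear on the DLT count. Item 3 excludes some and is unclear on others.
- That the DLT definition is itself inconsistent. The items in Section 6.1.4 and Appendix F agree.
- That toxicity goes unmonitored after day 42. Weekly monitoring to day 56 is scheduled; two sections fail to match it.

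**What to change.** Delete the grade-4-only list in Section 8.4.3.3, or align it with Sections 8.4.3.1, 8.4.4 and 8.4.5, so that grade, onset and resolution are recorded for every grade 3-5 event. The change should apply to the whole adverse-event reporting period. Suspending the list only during the DLT window would protect the DLT count but leave 8.4.3.3 in conflict with the general rule for the rest of follow-up, which can run to 1 year.

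Reconcile the toxicity-assessment schedules in Sections 6.1.3.1 and 8.4.3.3 with the synopsis, Section 1.3 and Section 8.1.

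The cost is protocol and CRF wording plus modest extra data entry for at most 28 patients. Weekly adverse-event monitoring and metabolic panels to day 56 are already scheduled, so no visit or test is added.
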